5.3 Treatment of subjects

Subjects will be randomised in a 2:2:1 ratio to receive either NNC0195-0092 (approximately 112 subjects), Norditropin[®] FlexPro[®] (approximately 112 subjects, open label towards both other arms) or placebo (approximately 56 subjects, double blind towards NNC0195-0092).

Time of injections:

- NNC0195-0092 and placebo subjects will inject themselves once a week s.c. in the morning no later than 10 AM to ensure consistency of PK/PD with previous trials. On site visit days this can be extended until 12:00 PM (noon). Trial drug must not be administered in the morning before relevant visit procedures have been performed (see section [2](#)).
- Norditropin[®] FlexPro[®] subjects will inject themselves daily s.c. in the evening (to reflect standard treatment practice) throughout the trial and only in the morning (no later than 12 PM and at least 12 hours after injection the evening before) during observed trial drug administration. Injections with Norditropin[®] FlexPro[®] the night before blood sampling for anti-hGH antibodies must occur at least 12 hours prior to sampling.

For the first 35-week treatment period, the first dose will be administered by the subject on Day 0 (randomisation), and the last dose will be administered by the subject at home during Week 33. For the extension period, the first dose will be administered in the beginning of Week 35, and the last

dose will be administered by the subject at home during Week 86. No drug will be administered at the Week 34 and Week 87. The maximal treatment duration for a single subject is 86 weeks.

Subjects in all three arms will be trained in the use of the pen-injector and inject themselves under the supervision of the site staff at the visit and will inject themselves at home (see sections [2](#) and [8.7](#)).

Weight loss medications known to affect body weight substantially are not allowed during the trial.

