17.1 Sample size calculation

Under the assumption of a true mean difference of 2.5% between NNC0195-0092 and placebo and a standard deviation (SD) of 4.5% for the primary endpoint and based on a two-sided, two-sample t-test with a significance level of 5% and a 2:1 randomisation ratio between NNC0195-0092 and placebo, 104 subjects in the NNC0195-0092 treated group and 52 subjects in the placebo treated group completing the main trial should ensure 90% power for detecting a difference between NNC0195-0092 and placebo. The assumptions of a true mean difference of 2.5% between active treatment and placebo and a SD of 4.5% is slightly conservative to what is observed in similar trials. In a secondary comparison of the primary endpoint, it will be possible to expect with probability 0.87 that half the length of the 95% confidence interval (CI) constructed for the difference between NNC0195-0092 and Norditropin[®] FlexPro[®] will be at most 1.3% if additional 104 subjects are enrolled in the Norditropin[®] FlexPro[®] treated group, resulting in a total of 260 subjects to be included in the trial. Expecting at most 7% drop-out from the trial, 280 subjects should be included in the trial.

Simulations (10000 samples, analysis based on multiple imputation technique as described in section [17.3](#)) under the the assumption of a drop-out rate of 7% and an additional assumption that 50% of the subjects who do not complete the main trial contribute to the primary analysis with post-randomisation DXA data, gives 89% power for detecting a difference between NNC0195-0092 and placebo with 112 subjects in the NNC0195-0092 treated group and 56 subjects in the placebo treated group. If the assumptions are changed to a drop-out rate of 15% and all subjects who do not complete the main trial will have no post-randomisation DXA data, then simulations gives 78% power for detecting a difference between NNC0195-0092 and placebo.

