17.4.1.2 Safety endpoints

The following endpoints will be used to support the secondary objectives of evaluation of safety in both the main (up to week 35) and extension (up to week 88) trial periods:

- Incidence of adverse events, including injection site reactions
- Incidence of clinical technical complaints
- Occurrence of anti-NNC0195-0092 antibodies
- Changes from baseline in physical examination, ECG results and vital signs
- Changes from baseline in clinical laboratory test results including haematology, biochemistry, fasting glucose, fasting insulin, steady state beta cell function (%B) and insulin resistance (IR) (HOMA estimates), and HbA1c levels

Adverse events will be analysed using descriptive statistics. All adverse events with onset after the first administration of trial product and up until Week 34 will be included in the main trial period analysis. The adverse events will be summarised by treatment, MedDRA (Medical Dictionary for Regulatory Activities) system organ class and MedDRA preferred term. The descriptive statistics will include the number and percentage of subjects who experienced adverse events and the number of events. Adverse events will be listed by treatment and subject with information on severity, relationship to trial product and demographics. Adverse events with onset before first dosing will be reported in a separate listing.

All other safety endpoints will be analysed using descriptive statistics. Additionally, an exact logistic regression analysis on the event of experiencing at least one injection site reaction during the main trial period will be done with treatment, GHD onset type, sex, region, DM and sex by region by DM interaction as factors included in the model as factors and number of injections taken in the main trial period included as offset.

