2.1.36 Section 17.4.1.2 Safety endpoints

Adverse events will be analysed using descriptive statistics. All adverse events with onset after the first administration of trial product and up until Week 354 will be included in the main trial period analysis.

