1.2 Scope of the statistical analysis plan

This SAP version 2.0 is based on the protocol REAL 1, version 6.0. The SAP describes in details the updated planned analysis of the TRIM-AGHD based endpoints and the reason for the update of the analysis and a detailed description of the planned analysis of supportive secondary endpoint body weight.

2 Statistical considerations

From the protocol, section 17.4.1 Supportive secondary endpoints, page 91 , updated analysis text is written in italic:

Changes in scores of TRIM-AGHD (total and individual domain scores), SF-36 (physical and health component summary scores and individual domain scores) from baseline to the 8, 25, and 34 week's measurements will be analysed using a mixed model for repeated measurements (MMRM), with treatment, GHD onset type, sex, region, DM and sex by region by DM interaction as factors and baseline value as a covariate, all nested within week as a factor. An unstructured covariance matrix will be used to describe the variability for the repeated measurements for a subject. From the MMRM the treatment differences at Week 34 between NNC0195-0092 and placebo and between NNC0195-0092 and Norditropin® FlexPro® will be estimated and the corresponding 95% CIs and p-values will be calculated for each endpoint. Subjects without post-randomisation data for the analysed endpoint will not be included in the analysis. *As a sensitivity analysis, the analysis of TRIM-AGHD endpoints will be repeated restricted to subjects who answered the new questionnaire at their visits (i.e. subjects with the following introductory text in the questionnaire "The following questions are about how your growth hormone deficiency (GHD) impacts your functioning and well-being. Please tick the response box that most closely represents your CURRENT EXPERIENCE with GHD. Please tick only one response box for each question. Remember there are no right or wrong answers to these questions").*

From the protocol, section 17.4.1 Supportive secondary endpoints, page 91, added text is written in italic:

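### The injection-site-reaction model uses the untransformed injection count as its offset, which adds about 204 to the NNC0195-0092 versus Norditropin log odds ratio

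*Protocol*

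**What the plan says.** Protocol section 17.4.1.2 summarises safety endpoints descriptively and adds one model: "an exact logistic regression analysis on the event of experiencing at least one injection site reaction during the main trial period will be done". Its factors are treatment, onset type, sex, region, diabetes status and the three-way interaction of the last three, with the "number of injections taken in the main trial period included as offset". No transformation of the count is mentioned. The section names no particular treatment contrast.

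Section 5.3 sets the injection frequencies. For the weekly arms: "NNC0195-0092 and placebo subjects will inject themselves once a week s.c. in the morning". For Norditropin: "subjects will inject themselves daily s.c. in the evening". Dosing starts on Day 0, and in the main period "the last dose will be administered by the subject at home during Week 33".

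Nothing supplied changes the offset. Item 2.1.36 of the amendment to protocol version 2.0 alters only the adverse event window of this section ("up until Week 354 will be included in the main trial period analysis", where the mark-up runs the old and new week digits together). The SAP covers TRIM-AGHD and body weight only. It also says: "This SAP version 2.0 is based on the protocol REAL 1, version 6.0". The full text of section 17.4.1.2 in version 6.0 is not among the documents.

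**The concern.** An offset is a term whose coefficient is fixed at 1, not estimated. Entering a raw count on the logit scale asserts that every further injection multiplies the odds of ever having a reaction by e. Because the count is nearly determined by the dosing schedule, the offset is close to a function of treatment arm. The arm coefficient must then absorb the whole gap in counts between weekly and daily dosing.

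Injection site reactions are part of a key safety endpoint. Section 5.2 gives comparison of local tolerability with daily Norditropin as a reason for the active arm. This is the only planned model that compares the reactions between arms. Followed literally, its weekly-versus-daily result would be dominated by the number of scheduled injections.

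**Working it through.** The documents give no numerical figure for this model, so there is none to reproduce.

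**Inputs**
- Weekly arms: 1 injection per week; Norditropin: 7 per week (section 5.3).
- Dosing weeks 0 to 33, which is 34 weeks (section 5.3).
- Planned arm sizes 112, 112 and 56 (section 5.3).
- Assumed: one injection per dose and, at first, full adherence.

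**Counts.** Weekly: 34 × 1 = 34. Daily: 34 × 7 = 238, or 33 × 7 + 1 = 232 if the last daily dose falls on the first day of Week 33.

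**Algebra.** The model is logit(p) = offset + α + β(arm) + covariates. If the offset equals a constant c(arm) within each arm, c(arm) + β(arm) plays the role of the arm coefficient in the model without an offset. Hence

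β(NNC) − β(Nord) = log OR without offset + c(Nord) − c(NNC).

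This is a reparametrisation, so it holds with any covariates and for both maximum likelihood and exact estimation.

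- NNC0195-0092 versus Norditropin: 238 − 34 = 204 (or 232 − 34 = 198). As an odds ratio, e^204 is about 10^88.6.
- NNC0195-0092 versus placebo: 34 − 34 = 0.

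**Exact conditional results, 112 versus 112, assumed numbers of reactors**

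| Reactors NNC / Norditropin | No offset: log OR (95% CI) | Raw-count offset |
|---|---|---|
| 11 / 11 | 0.0 (-0.98 to 0.98) | 204.0 (203.0 to 205.0) |
| 1 / 60 | -4.83 (-8.55 to -3.02) | about 199.2 (each figure plus 204) |

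In the second row, data strongly favouring the weekly product are reported as an enormous excess against it.

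**p-value.** Under a null coefficient, the offset puts almost all probability on every reactor being in the daily arm. With 0 versus 60 reactors, exact p is 1. With 1 versus 60, the observed split relative to 0 versus 61 has weight 112 × C(112,60)/C(112,61) × e^-204 = 112 × 61/52 × 10^-88.6, or about 131 × 10^-88.6. So p is below 10^-80. One reactor on NNC0195-0092 moves the test from one extreme to the other.

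**Imperfect adherence.** Scaling both counts equally gives shifts of 0.9 × 204 = 183.6 and 0.8 × 204 = 163.2. Simulated maximum-likelihood fits (not exact) assumed 10% incidence, equal random missed doses in all arms and 7% drop-out. The drop-out rate is the planning bound in section 17.1 ("Expecting at most 7% drop-out from the trial"). Median log odds ratios were 201.0, 195.9, 186.5 and 167.5 at 2%, 5%, 10% and 20% missed doses. Adjusting for the listed factors, with an assumed covariate mix, gave 204.0 at full adherence, 186.4 at 10% and 167.4 at 20%.

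**Log offset instead.** The shift becomes ln(238/34) = ln 7 = 1.95. With 11/112 in each arm the ratio is 7, under a logit or a complementary log-log link alike. That is the correct per-injection answer: equal proportions reacted on one seventh of the injections.

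The links differ when per-injection risk is equal. With weekly incidence pN, daily incidence is pD = 1 − (1 − pN)^7. The logit model with log offset then estimates exp[logit(pN) − logit(pD) + ln 7], where 1.00 would be right:

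| Assumed weekly incidence | 2% | 5% | 10% | 20% |
|---|---|---|---|---|
| Logit, log offset | 0.94 | 0.85 | 0.71 | 0.46 |
| Complementary log-log, log offset | 1.00 | 1.00 | 1.00 | 1.00 |

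**The case against.** The strongest reply is that a one-sentence protocol summary uses the count as shorthand for an exposure offset, conventionally on the log scale, and that a log odds ratio of 204 could not slip unnoticed into a report. That is plausible, and it makes the likely defect small. But the log is not written. The protocol does state log transformation for lipids, hsCRP and IL-6, although those are response variables. If the problem surfaced only when the output looked absurd, the choice among no offset, a log offset and another link would be made with data in hand. That choice can change the sign of the result.

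Two further points stand. Adjusting for injections taken is a legitimate aim, so removing the offset changes the question and is not simply a correction. And the adherence results are maximum likelihood under assumed rates, not the planned exact method.

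Two stronger readings are tempting, and neither is supported. A reader might infer that the fitted odds ratio contains nothing about the reactions. With constant counts it is the ordinary log odds ratio plus a known constant, so it is mislocated, not empty. A reader might also infer that a log offset is equally faulty because it builds in a factor of 7. Any per-injection model gives 7 when equal proportions react; that is its estimand, not bias. The remaining reservation about a log offset in the logit model is link distortion when reactions are common.

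**Conclusion.** The point holds for the text as written. An untransformed count as offset adds about 204 (198 under the shorter daily count) to the NNC0195-0092 versus Norditropin log odds ratio at full adherence. The reported odds ratio, its sign and its p-value are then uninterpretable for that contrast. The algebra needs only injection counts that are constant within each arm, with one injection per dose. Under the assumed missed-dose rates up to 20%, the shift is still well over 160. NNC0195-0092 versus placebo has no systematic shift when adherence is equal.

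It would go too far to conclude that the trial's main result or its whole safety evaluation is compromised. This is a supportive model. The primary endpoint, the sample size and the descriptive adverse event tables do not depend on it. Nor can it be said that the final protocol carries the fault, because section 17.4.1.2 of version 6.0 is not shown.

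**What to change.** Before the main-trial database lock, check section 17.4.1.2 in protocol 6.0. If the untransformed count is still the offset, replace it and state the estimand:

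- **Per-subject risk:** fit treatment and the listed factors with no offset, and report the adjusted odds ratio. This keeps the exact logistic method but gives up adjustment for exposure.
- **Per-injection risk:** use log(number of injections) as offset, preferably with a complementary log-log link for one or more reactions, or a Poisson or negative binomial model for the number of reactions. These are no longer exact logistic regression. If the logit link is kept with a log offset, say that it approximates the per-injection ratio only when reactions are rare.

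If both are wanted, label them separately, since the same data can give 1 per subject and 7 per injection. The cost is one or two sentences in the protocol or SAP; no new data are needed.

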17.5 Interim reporting, reporting of main and extension periods of the trial

Two partial database locks are planned during the trial (facilitating interim safety reporting and analysis of main trial period data, respectively) as well as a database lock after the extension period of the trial is completed (facilitating the analysis of the extension trial data).

First partial DBL

A blinded interim safety reporting will be performed when 50 subjects randomised to NNC0195-0092 have completed the main trial.

Data for all subjects up to and including V15 who have completed the main trial at this time will be included in a partial database lock (first partial database lock of trial data) with the following exceptions:

- Data derived from the DXA body composition measurement will not be included (see section [8.4.1](#))
- Antibody samples will be fully analysed but not be loaded in the clinical database to avoid unblinding
 - Anti-drug antibody data for non-neutralising antibodies against NNC0195-0092 and hGH not classified as high titre antibodies (see section [8.5.13](#)) will be reported as a tabulated summary in a blinded manner. This will include number of subjects with antibodies in the once weekly arms (NNC0195-0092 + placebo) versus number of subjects with antibodies in the once daily arm (hGH) including antibody titres and results for in vitro neutralising effect. Handling of data and report preparation is the responsibility of the analysing laboratory
 - Should any subjects develop high titre and/or persistent in vitro neutralising antibodies (see section [8.5.13](#)) the safety committee might recommend unblinding of specific data for further analysis and an independent ad hoc safety group (see section [12.7.1](#)) will be established. The purpose of an ad hoc safety group is to review unblinded data and based on analyses recommend further action to the safety committee. This ad hoc group will be able to report relevant data in an unblinded manner. Ad hoc safety group members must NOT be involved in daily project activities
 - Data for PK, IGF-I, IGFBP-3 will be fully analysed to support the independent ad hoc safety group if needed but data will not be loaded in the clinical database to avoid unblinding.

Data will be analysed using descriptive statistics and will support the future phase 3 trial programme in children with GHD (regulatory requirement). As the safety data will be reported in a blinded manner (once weekly arms combined (NNC0195-0092 or placebo) versus Norditropin[®] FlexPro[®]) no impact is expected on the remainder of the trial.

Second partial DBL (main trial)

Data for all subjects up to and including V15 who have completed or discontinued the main trial will be included in a partial database lock (second partial database lock of trial data). After the second partial DBL the sponsor will become unblinded while the subjects and site personnel will remain blinded regarding the NNC0195-0092 versus Placebo allocation during the main period.

Final DBL (extension)

The extension trial is open-label after the main trial period and the data from the extension period will support the secondary objective of evaluating the efficacy and safety of NNC0195-0092 for up to 86 weeks of treatment in adults with GHD, but will not contribute with confirmatory results.

17.6 Population PK analysis

A population pharmacokinetic analysis (POP-PK) will be used to evaluate the effect of anti-NNC0195-0092 antibodies on the PK of NNC0195-0092. All values from samples taken 3 days after the last trial drug administration will be used for the analysis and relevant covariates that could influence the PK will be included in the analysis.

A more technical and detailed elaboration of the population pharmacokinetic analysis will be done in the modelling analysis plan (MAP) which will be finalised before the second DBL. Results will be reported in a report separate from the CTR.

